## 6.4.3 Vital Signs and Physical Measurements

Vital signs include systolic blood pressure, diastolic blood pressure, heart rate, temperature, and respiratory rate. Physical measurements include height, weight, and body mass index (BMI). These parameters are measured with both measurement date and time at early termination and all visits except Weeks 2 and 14; height is measured at Screening only.

Refer to the Core SAP for TLF contents.

# 6.4.3.1 Vital Sign and Physical Measurement Changes from Baseline over Time

The table of values and changes from baseline in vital signs and physical measurements is provided by treatment group, zavegepant pooled, placebo pooled, and overall for the safety analysis set at the following time points: baseline; each scheduled visit through Week 12 and EOT in the on-DBT safety analysis period; each scheduled visit from Week 14 through Week 64 and EOT in the on-OL zavegepant safety analysis period; each scheduled visit in the follow-up safety analysis period. Results for zavegepant pooled and placebo pooled are displayed at baseline and time points in the on-DBT safety analysis period. Results for overall are displayed only at baseline and time points in the on-OL zavegepant and follow-up safety analysis periods.

Refer to the Core SAP for (1) handling multiple values in an analysis visit window or on the same measurement date, and (2) deriving the EOT value in an on-treatment safety analysis period.

## 6.4.3.2 Vital Sign and Physical Measurement Abnormalities

Frequency tables of vital sign and physical measurement abnormalities are provided for the following safety analysis periods and analysis sets:

- On-DBT for the DBT safety analysis set
- On-OL zavegepant for the OL zavegepant safety analysis set
- Follow-up for the follow-up safety analysis set.

## 6.4.4 Electrocardiograms

ECG parameters include RR, QRS, PR, QT, QTcB, QTcF, and ventricular heart rate. ECGs are measured with both acquisition date and time at the following visits: Screening; Weeks 4, 12, 16, 24, 48, and 64; and early termination. ECGs are analyzed using results from local tests reported on ECG CRFs and the external central vendor Bioclinica. Note that the ECG CRF collects RR in sec, not msec.

Refer to the Core SAP for TLF contents.

#### 6.4.4.1 ECG Changes from Baseline over Time

The table of values and changes from baseline in ECG parameters is provided by DB treatment group, zavegepant pooled, placebo pooled, and overall for the safety analysis set at the following time points: baseline; each scheduled visit through Week 12 and EOT in the on-DBT safety analysis period; and each scheduled visit from Week 16 through Week 64 and EOT in the on-OL zavegepant safety analysis period. Results for zavegepant pooled and placebo pooled are displayed only at baseline and time points in the on-DBT safety analysis period. Results for overall are displayed only at baseline and time points in the on-OL zavegepant safety analysis period.

Refer to the Core SAP for (1) handling multiple values in an analysis visit window, and (2) deriving the EOT value in an on-treatment safety analysis period.

If there are multiple values on the same measurement date, then the following hierarchy is used to further break ties as available:

- Last central value collected timewise with the last ECG reference identifier
- Last local value collected timewise with the last entry date/time.

#### 6.4.4.2 ECG Abnormalities

Frequency tables of ECG abnormalities are provided for the following safety analysis periods and analysis sets:

- On-DBT for the DBT safety analysis set
- On-OL zavegepant for the OL zavegepant safety analysis set
- Follow-up for the follow-up safety analysis set.

ECG abnormalities are presented together with vital sign and physical measurement abnormalities in the same tables (see Section 6.4.3.2).

#### 6.4.5 C-SSRS

The C-SSRS is a clinician administered questionnaire used to help immediate risk of suicide. The C-SSRS is administered at early termination and all visits except the Pre-randomization Laboratory Visit. At the Screening Visit, the recall period for completing is 12 months for suicidal ideation and 10 years for suicidal behavior; at all other visits, the recall period for completing the C-SSRS is since the last visit.

Frequency tables of C-SSRS suicidality are provided for the following safety analysis periods and analysis sets:

- On-DBT for the DBT safety analysis set
- On-OL zavegepant for the OL zavegepant safety analysis set
- Follow-up for the follow-up safety analysis set.

Refer to the Core SAP for calculation of C-SSRS parameters and TLF contents.

## 6.4.6 Safety Narrative Subject Identifiers

The by-subject listing of safety narrative subject identifiers is provided for the following select events, safety analysis periods, and analysis sets as columns:

- Death in any safety analysis period for the enrolled analysis set
- SAE during any of the following safety analysis periods and analysis sets:
  - o On-DB or OL zavegepant for the DB or OL zavegepant safety analysis set
  - Follow-up for the DB or OL zavegepant safety analysis set
- Non-SAE leading to study drug discontinuation in any safety analysis period for the DB or OL zavegepant safety analysis set
- Event of special interest on DB or OL zavegepant for the DB or OL zavegepant safety analysis set:
  - $\circ$  ALT or AST > 3x ULN
  - o ALT or AST > 3x ULN concurrent with TBL > 2x ULN
  - $\circ$  ALP or TBL > 2x ULN
  - Select hepatic-related non-SAE, i.e., PT containing cirrhosis, hepatic failure, hepatitis, jaundice, or liver failure
  - Cardiovascular non-SAE
  - Suicidality non-SAE.

Refer to the Core SAP for additional details.

#### 6.5 Outcomes Research

Analyses are based on as-randomized treatment group for the DBT efficacy analysis set.

Randomization strata used in analyses are based on actual data.

Outcomes research questionnaires and rating scales are MSQoL and MIDAS. These are assessed at Baseline, Week 12, Week 24, Week 64, and early termination. MSQoL and MIDAS are collected from respective CRFs with an assessment date.

Measurements are slotted into analysis periods and analysis visits using the following steps:

- 1) Measurements are slotted into the pretreatment, DBT outcomes research, and OL zavegepant outcomes research analysis periods.
- 2) Measurements are slotted into analysis visits in the analysis periods listed in the previous step (see Table 5).

See Sections 6.2.5, 7.2 and 7.3 for definitions of baseline, outcomes research analysis periods, and analysis visit windows, respectively.

A confidence level of 97.5% is used for CIs.

The by-subject listing of MSQoL and MIDAS is provided for the enrolled analysis set, and displays values and changes from baseline in MSQoL domain scores and MIDAS total, absenteeism, and presenteeism scores.

Refer to the Core SAP for the following: detailed descriptions of these questionnaires; calculating scores and imputing missing data; deriving categories; handling multiple questionnaires values in an analysis visit window or on the same assessment date; and TLF contents.

#### 6.5.1 MSQoL

The MSQoL consists of 14 items across the following 3 domains: (1) restrictive role function, (2) preventative role function and (3) emotional function.

Refer to the Core SAP for calculating domain scores and imputing missing data.

## **Descriptive Analyses**

The table of values and changes from baseline in scores are provided for each domain by treatment group, placebo pooled, and overall for the DBT efficacy analysis set at the following time points: baseline; Week 12 in the DBT outcomes research analysis period; Week 24 and Week 64 in the OL zavegepant outcomes research analysis period. Results for placebo pooled are displayed only at baseline and time points in the DBT outcomes research analysis period. Results for overall are displayed only at baseline and time points during the OL zavegepant outcomes research analysis period.

The frequency table of MSQoL domain score increase from baseline categories is provided by treatment group and overall for the DBT efficacy analysis set at the following time points: Week 12 in the DBT outcomes research analysis period; Week 24 and Week 64 in the OL zavegepant outcomes research analysis period. Results for placebo pooled are displayed only at baseline and

time points in the DBT outcomes research analysis period. Results for overall are displayed only at baseline and time points during the OL zavegepant outcomes research analysis period.

Results support exploratory objective #12.

#### **Treatment Group Comparisons**

Analysis of the restrictive role function domain is based on the DBT efficacy analysis set with paired data, i.e., restrictive role function domain scores at both baseline and Week 12 of the DBT outcomes research analysis period.

Treatment groups are compared using a linear regression model with the following attributes:

- Variables: Week 12 change from baseline in the score as the dependent variable; baseline score as a covariate; treatment group and randomization stratum as fixed effects.
- SE estimation method: See Section 6.3.1.3.

The table provides n (i.e., number of subjects with paired data) and the following model estimates:

- LSM change from baseline at Week 12, SE, and 97.5% CI for each treatment group and placebo pooled
- Difference in LSM changes from baseline at Week 12 between each zavegepant treatment group and placebo pooled (zavegepanti – placebo pooled; i = 100 and 200), SE, and 97.5% CI.

Results support secondary objective #5.

See Section 9.3.2 for example SAS code. Model estimates by randomization stratum (yes, no) are presented in the same table, using additional models that exclude randomization stratum as a fixed effect.

#### 6.5.2 MIDAS

The MIDAS is a retrospective, patient-administered, 5-item questionnaire that measures headache-related disability as lost time due to headache from paid work or school, household work, and non-work activities.

Refer to the Core SAP for calculating MIDAS scores (i.e., total, absenteeism, presenteeism, item) and imputing missing data.

#### **Descriptive Analyses**

The table of values and changes from baseline in total, absenteeism, presenteeism, and item scores is provided, and has a similar format as the one described in Section 6.5.1.

Results support exploratory objective #12.

#### **Treatment Group Comparisons**

Analysis of the total score is based on the DBT efficacy analysis set with total scores at both baseline and Week 12 of the DBT outcomes research analysis period.

Treatment groups are compared using a linear regression model with the same attributes as the one described in Section 6.5.1. The table has the same format.

Results support secondary objective #6.

## 7 CONVENTIONS

#### 7.1 Derived Dates

Derived dates are defined as follows:

- eDiary measurement date: Complete datepart{eDiary finding date/time} 1 day, if from the eDiary headache log; complete datepart{eDiary finding date/time} otherwise
- eDiary efficacy data date: eDiary measurement date from the eDiary headache log
- Study drug start date: Earliest complete study medication start date from IP Dosing CRF records with number of capsules taken > 0. This is an analysis period reference date.
- Imputed study medication end date: If the study medication end date is (1) non-complete or (2) complete but before the study medication start date, then the imputed end date is set to the study medication start date. Otherwise, the imputed end date is set to the complete study medication end date. Derived only for IP Dosing CRF records with complete study medication start date and number of capsules taken > 0.
- Study drug end date: Latest of (1) complete study medication start dates, or (2) complete study medication end dates from IP Dosing CRF records with number of capsules taken > 0
- Study drug last date:
  - O Before the final database lock: Study drug end date derived only for subjects who have either (1) or (2):
    - (1) "Yes" or "no" response to the phase completion question on the DB Subject Status CRF, and {either (1a) "no" response to the continuing to the Follow-up Phase question on the DB Subject Status CRF, or (1b) "no" response to the continuing to the next phase question on the DB Subject Status CRF, or (1c) "Follow-up" specified as the next phase on the DB Subject Status CRF}, and missing OL zavegepant start date
    - (2) "Yes" or "no" response to the phase completion question on the OLE Subject Status or Follow-up Subject Status CRF
  - o Final database lock: Study drug end date

This is an analysis period reference date.

• DB study drug start date: Earliest complete study medication start date from IP Dosing CRF records with number of capsules taken > 0 and valid DB wallet ID. This is an analysis period reference date.

- DB study drug end date: Latest of (1) complete study medication start date, or (2) complete study medication end date from IP Dosing CRF records with number of capsules taken > 0 and valid DB wallet ID
- DB study drug last date:
  - Before the CSR database lock: DB study drug end date derived only for subjects with "yes" or "no" response to the phase completion question on the DB Subject Status, OLE Subject Status, or Follow-up Subject Status CRF
  - CSR database lock or after: DB study drug end date

This is an analysis period reference date.

- OL zavegepant start date: Earliest complete study medication start date from IP Dosing CRF records with number of capsules taken > 0 and valid OL wallet ID. This is an analysis period reference date.
- OL zavegepant end date: Latest of (1) complete study medication start date, or (2) complete study medication end date from IP Dosing CRF records with number of capsules taken > 0 and valid OL wallet ID
- OL zavegepant last date:
  - Before the final database lock: OL zavegepant end date derived only for subjects with "yes" or "no" response to the phase completion question on the OLE Subject Status or Follow-up Subject Status CRF
  - Final database lock: OL zavegepant end date

This is an analysis period reference date.

- DB or OL zavegepant start date: Study drug start date for subjects whose as-treated DB treatment group is zavegepant; OL zavegepant start date for subjects whose as-treated DB treatment group is placebo. This is an analysis period reference date.
- DB or OL zavegepant end date: Study drug end date for subjects whose as-treated DB treatment group is zavegepant; OL zavegepant end date for subjects whose as-treated DB treatment group is placebo
- DB or OL zavegepant last date: Study drug last date for subjects whose as-treated DB treatment group is zavegepant; OL zavegepant last date for subjects whose as-treated DB treatment group is placebo. This is an analysis period reference date.
- OP start date: Earliest of the following: screening visit date 1 day; eDiary efficacy data date. The screening visit date is determined from the visit label from the Visit Date CRF. This is an analysis period reference date.
- OP end date:
  - $\circ$  If the study drug start date is not missing: study drug start date -1 day
  - If the study drug start date is missing and the randomization date is not missing: randomization date − 1 day

- If both study drug start date and randomization date are missing: Last contact date This is an analysis period reference date.
- Last contact date:
  - 1. Earliest complete death date from the AE CRF, if it exists.
  - 2. Otherwise, the latest complete date of the following: AE start or end; ECG; eDiary finding; informed consent; IWRS randomization; laboratory test collection; non-study medication start or end; physical exam; physical measurement; procedure; rating scale; questionnaire; study medication start or end; vital sign; visit.
  - 3. If the last contact date is after the most recent raw database creation date, then it is set to the most recent raw database creation date.
- Death date: refer to the Core SAP.

No imputations are performed on these derived dates, unless specified otherwise.

Refer to the Core SAP for the definition of complete dates.

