# 4 ANALYSIS SETS, TREATMENT GROUPS, AND SUBGROUPS

# 4.1 Analysis Sets

The following analysis sets are evaluated and used for presentation and analysis of the data:

- Enrolled: Subjects who sign an informed consent form and are assigned a subject identification number, i.e., nonmissing informed consent date. This analysis set is used mainly to assess study population and in by-subject listings.
- Full: Subjects in the enrolled analysis set who receive a randomized treatment assignment from the IWRS, i.e., nonmissing IWRS randomization date. This analysis set is used mainly to assess study population.
- Safety: Subjects in the enrolled analysis set who take ≥ 1 dose of study drug (zavegepant or placebo), i.e., nonmissing study drug start date. This analysis set is used to assess study population and produce select by-subject listings.
  - O DBT safety: Subjects in the safety analysis set who take ≥ 1 dose of DB study drug (zavegepant or placebo), i.e., nonmissing DB study drug start date. This analysis set is used to assess study population, exposure, and on-DBT safety.
  - OL zavegepant safety: Subjects in the safety analysis set who take ≥ 1 dose of OL zavegepant, i.e., nonmissing OL zavegepant start date. This analysis set is used to assess study population, exposure, and on-OL zavegepant safety.
    - Interim safety: Subjects in the OL zavegepant safety analysis set with OL zavegepant start date DB study drug last date > 7 days. This analysis set is used to assess post-DBT pre-OL zavegepant safety.
  - DB or OL zavegepant safety: Subjects in the safety analysis set who take ≥ 1 dose of DB or OL zavegepant, i.e., nonmissing DB or OL zavegepant start date. This analysis set is used to assess exposure and on-DB or OL zavegepant safety.
  - o Follow-up safety: Subjects in the safety analysis set whose last contact date is in the follow-up safety analysis period. This analysis set is used to assess follow-up safety.
- DBT efficacy: Subjects in the full analysis set who are randomized only once and take ≥ 1 dose of DB study drug (zavegepant or placebo). This analysis set is used mainly to assess DBT outcomes research.

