## 4.2 Treatment Groups

Treatment groups in the DBT Phase are zavegepant 100 mg, zavegepant 200 mg, placebo 100 mg, and placebo 200 mg. OL zavegepant dose groups in the OLE Phase are zavegepant 100 mg and zavegepant 200 mg.

The safety analysis sets are assessed by as-treated treatment group (i.e., actual treatment received), the randomized, full, efficacy, and migraine analysis sets are assessed by as-randomized treatment group, and the enrolled analysis set is assessed overall.

If a subject takes  $\geq 1$  dose of planned randomized DB study drug, then that subject is considered to have as-treated treatment group equal to as-randomized treatment group (see Section 6.2.6.2).

If there are non-randomized subjects who take study drug, then the as-randomized treatment group of "not randomized" is included in the full analysis set augmented with the safety analysis set.

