## **DB** or **OL Zavegepant** Exposure

The table of DB or OL zavegepant exposure is provided descriptively by DB or OL zavegepant dose and overall for the DB or OL zavegepant safety analysis set, and summarizes the following parameters descriptively as continuous or categorical variables:

- Time on DB or OL zavegepant (weeks), derived as (DB or OL zavegepant end date DB or OL zavegepant start date + 1)/7
- Time on DB or OL zavegepant (weeks) categories:  $\leq 12, \leq 24, \geq 24$
- Time on DB or OL zavegepant milestone categories:
  - $\circ$   $\geq$  3 months, defined as  $\geq$  11 weeks
  - $\circ$   $\geq$  6 months, defined as  $\geq$  23 weeks
  - $\circ$   $\geq$  1 year, defined as  $\geq$  51 weeks
  - $\circ$  ≥ 15 months, defined as ≥ 63 weeks.
- Cumulative DB or OL zavegepant exposure (mg), derived as {number of days × number of capsules taken per day × 25} across records with complete study medication start date and kit type identifier of DB zavegepant 100 mg, DB zavegepant 200 mg, OL zavegepant 100 mg, or OL zavegepant 200 mg
- Average DB or OL zavegepant exposure (mg per day), derived as cumulative DB or OL zavegepant exposure/time on DB or OL zavegepant drug (days)
- Total DB or OL zavegepant exposure (capsules) summed across all subjects, derived by summing cumulative DB exposure across all subjects
- Total DB or OL zavegepant exposure (patient-years), derived by summing (DB or OL zavegepant end date DB or OL zavegepant start date + 1)/365.25 across all subjects.

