## 6.2.6.2 Measurements of Treatment Compliance

## **DB** Treatment Compliance

DB treatment compliance categories are defined as follows for relevant protocol deviations (see Sections 6.2.4.1 and 9.1):

- DB study drug taken but not randomized
- DB capsule count compliance < 80% from DB study drug start to later of last scheduled DBT Phase visit or DB study drug end/OL zavegepant start. Capsule count compliance is derived as 100 × actual cumulative DB capsule count/required cumulative DB capsule count, where
  - Actual cumulative DB capsule count is derived by summing the {number of days × number of capsules taken per day} across records with complete study medication start date and valid DB wallet ID.
    - Number of days for a record is derived as imputed study medication end date study medication start date + 1.
  - Required DB cumulative capsule count is derived as {DB maxdate DB study drug start date + 1} × {required number of capsules per day}, where
    - DB maxdate is defined as the latest of the (1) scheduled Week 2, 4, 8, and 12/EOT visit dates, and (2) DB study drug end date. Scheduled visits are identified from visit labels from the Visit Date CRF, and therefore exclude those containing "unscheduled" in the visit label.
    - If DB maxdate  $\geq$  OL zavegepant start date, then DB maxdate is set to OL zavegepant start date -1 day.
    - The required number of capsules per day is 4 for subjects in the zavegepant 100 mg or matching placebo group, and 8 for subjects in the zavegepant 200 mg or matching placebo group.
- More than the required number of DB capsules per day taken on any 1 day. This is determined from either of the following:
  - Records with complete study medication start date, valid DB wallet ID, and number of capsules taken per day > required number of capsules per day.
  - Overlapping records with valid DB wallet ID (see Section 9.4).
- Incorrect DB study drug taken
  - All the time. Defined as as-treated treatment group not equal to as-randomized treatment group, i.e., either of the following:
    - Subjects randomized to zavegepant who took  $(1) \ge 1$  capsule from a DB placebo wallet, and (2) no capsules from a DB zavegepant wallet
    - Subjects randomized to placebo who took  $(1) \ge 1$  capsule from a DB zavegepant wallet, and (2) no capsules from a DB placebo wallet.

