 At least once. Defined as (1) subjects randomized to zavegepant who took ≥ 1 capsule from a DB placebo wallet, or (2) subjects randomized to placebo who took ≥ 1 capsule from a DB zavegepant wallet.

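### SAP 7.1 dates zavegepant exposure by as-treated group, so a placebo-randomized subject who took both placebo and active double-blind capsules is left out of the any-zavegepant safety set or dated late

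*SAP*

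**What the plan says.** Four SAP rules meet here.

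- **Set (SAP 4.1).** The DB or OL zavegepant safety set is "Subjects in the safety analysis set who take ≥ 1 dose of DB or OL zavegepant, i.e., nonmissing DB or OL zavegepant start date". Protocol 9.2 defines the same set by at least one dose and attaches no as-treated condition.
- **Dates (SAP 7.1).** The rule reads "DB or OL zavegepant start date: Study drug start date for subjects whose as-treated DB treatment group is zavegepant". For the rest it is "OL zavegepant start date for subjects whose as-treated DB treatment group is placebo". The end and last dates split the same way. The start and last dates are analysis period reference dates.
- **As-treated group (SAP 4.2 and 6.2.6.2).** Once a subject takes one dose of the planned double-blind drug, "then that subject is considered to have as-treated treatment group equal to as-randomized treatment group". Section 6.2.6.2 changes the group only when no capsule came from the planned kind of wallet. It lists a separate deviation for taking the wrong drug at least once, whose second limb is "2) subjects randomized to placebo who took ≥ 1 capsule from a DB zavegepant wallet".
- **Exposure (SAP 6.2.6.1).** Time on DB or OL zavegepant is the span between the derived dates. Cumulative milligrams are summed over records with a "kit type identifier of DB zavegepant 100 mg, DB zavegepant 200 mg" or either open-label kit type, whatever the as-treated group.

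**The concern.** Membership of a set meant to hold everyone exposed to zavegepant depends on a group label, not on the dosing records. The label is decided by whether any planned dose was taken, which is a different question from whether zavegepant was ever taken. The SAP anticipates subjects with both kinds of wallet, since it makes them a deviation category, but does not carry them into the derived dates.

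The set supplies the DB or OL zavegepant exposure table (SAP 6.2.6.1), an AE overview (6.4.1.2), an LFT elevation table (6.4.2.2) and the narrative identifiers for SAEs, discontinuations and events of special interest (6.4.6). A subject outside the set with ALT above 3 times ULN after active capsules would not be flagged there for a narrative.

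**Working it through.** The plan gives no figure to reproduce. The check follows the rules for each kind of placebo-randomized subject, then puts numbers on an invented example. The documents report no actual mis-dispensed subject.

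**Rules applied**

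1. Placebo capsules only: as-treated placebo, start date equal to the open-label start. Correct.
2. Active double-blind capsules only: as-treated group becomes zavegepant (6.2.6.2), start date equal to the first dose. Correct.
3. Both kinds, no open-label drug: as-treated placebo, start date missing. Not in the set, although its description is met.
4. Both kinds, then open-label drug: as-treated placebo, start date equal to the open-label start. In the set, but dated late.

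**Invented example.** A placebo 100 mg subject takes 4 capsules of 25 mg a day: placebo on days 1–28, an active double-blind kit on days 29–56, placebo on days 57–84. If the subject continues, open-label zavegepant 100 mg runs on days 91–454.

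- Active double-blind amount: 28 × 4 × 25 = 2,800 mg.
- Open-label amount: (454 − 91 + 1) × 4 × 25 = 364 × 100 = 36,400 mg.
- Total by kit type if the subject continues: 39,200 mg.

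Without open-label drug, the SAP leaves this subject out of the set despite 2,800 mg taken. With open-label drug, the start date is day 91 against a first active dose on day 29, which is 91 − 29 = 62 days late. Average exposure for the continuing subject is:

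| Rule | Start | Days in denominator | mg/day |
|---|---|---|---|
| SAP dates | 91 | 364 | 39,200 / 364 = 107.7 |
| Kit-based dates, start-to-end span | 29 | 454 − 29 + 1 = 426 | 39,200 / 426 = 92.0 |
| Kit-based, zavegepant dosing days | 29 | 28 + 364 = 392 | 39,200 / 392 = 100.0 |

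The assigned rate is 100 mg/day. Changing the dates alone turns an overstatement into an understatement, because 426 − 392 = 34 days without zavegepant (days 57–90) enter the span. Only the third row recovers the rate.

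**Size of one error.** A wallet holds 32 capsules (SAP 6.2.6.1): 32 / 4 = 8 days at 100 mg, or 32 / 8 = 4 days at 200 mg. In either case it is 32 × 25 = 800 mg. With one wrong 100 mg wallet and 364 open-label days, the SAP average is (800 + 36,400) / 364 = 102.2 mg/day, about 2% too high. Subjects receive 2 + 2 + 4 + 4 = 12 wallets at 100 mg, or 4 + 4 + 8 + 8 = 24 at 200 mg, over the double-blind phase (Protocol Table 1).

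**The case against.** Assigning whole subjects by the as-treated rule is a stated convention. It applies equally to zavegepant subjects who took some placebo, and it is reasonable for comparing arms. The subjects in question are reported as a protocol deviation (SAP 9.1). That stands for the between-arm tables. It does not make the rule a suitable test of whether someone ever took zavegepant, which is what SAP 4.1 and Protocol 9.2 ask.

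Three stronger readings are tempting, and the documents do not support them.

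- **That any placebo subject given an active wallet drops out.** A subject who took only active capsules is re-classed and dated correctly.
- **That events are lost from the report.** They are tabulated in the DBT safety set under placebo. The AE listing and the listing of select LFT elevations cover the enrolled set (6.4.1, 6.4.2), the LFT plots cover the whole safety set (6.4.2.2), death narratives use the enrolled set (6.4.6), and the study drug listing shows kit type (6.2.6.1).
- **That some 12 weeks of exposure is typically at stake.** That is a ceiling. It would need almost every wallet to be wrong while at least one placebo capsule was still taken.

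The set also matters less than it did. In the current SAP, the estimands for secondary objectives 7–9 name only the DBT and OL zavegepant safety sets (Table 2), although 6.4.2.2 still lists the DB or OL table among those supporting objective 8.

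Finally, SAP 7.2 leaves the safety period definitions to the Core SAP, which is not available here. How individual events are slotted cannot be confirmed. Set membership, the derived dates and the exposure formula are all in this SAP and can be.

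**Conclusion.** The inconsistency is real and minor. For placebo-randomized subjects who took both placebo and active double-blind capsules, the SAP's description of the set and its derivation disagree. Those who never take open-label zavegepant are left out; those who do are dated late, and their milligrams and time on drug do not match. The effect is confined to the DB or OL zavegepant exposure, AE overview and LFT tables and the non-death narrative identifiers, where events are missing or misattributed.

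The number of subjects is not given. That it is very small is an assumption, based on the error requiring a mis-dispensed wallet. The 107.7 mg/day figure depends on the invented four-week example; a single wrong 100 mg wallet gives 102.2. No efficacy result is affected.

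**What to change.** In SAP 7.1, derive the DB or OL zavegepant start, end and last dates, and hence membership of the set, from IP Dosing records with more than zero capsules taken and a DB or OL zavegepant kit type. Apply this to all subjects whatever their as-treated group. In SAP 6.2.6.1, compute average DB or OL zavegepant exposure over zavegepant dosing days, using the SAP 9.4 method restricted to zavegepant kit types, instead of the start-to-end span. As-treated grouping can stay for the between-arm safety tables.

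The cost is a few definitions and some reprogramming. Kit type is already merged by wallet ID, so no new data are needed. There are two side effects to state. For subjects with both kinds of wallet, some intervening placebo days will fall inside the on-zavegepant period, which should be footnoted. An average per dosing day no longer falls when doses are skipped, so the table should label it as such.
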